#### **5.4 REPORTING REQUIREMENTS FOR SAEs OR UADEs**

It is the responsibility of the Principal Investigator to report SAEs or UADEs to the sponsor within 24 hours. Reporting of the event to applicable regulatory bodies should occur per the established reporting criteria. For UADE reports, investigators are required to submit a report of a UADE to the sponsor and the reviewing IRB as soon as possible, but in no event later than 10 working days after the Investigator first learns of the event (§ 812.150(a)(1)). Sponsors must immediately conduct an evaluation of a UADE and must report the results of the evaluation to FDA, all reviewing IRBs, and participating investigators within 10 working days after the sponsor first receives notice of the effect (§§ 812.46(b), 812.150(b)(1)).

#### **5.5 MEDICAL TREATMENT FOR AEs, SAEs AND UADEs**

Medical treatment for adverse events during and following the study procedure will be at the discretion of the Investigator.

## 5.6 MEDICAL MONITOR

The Medical Monitor (independent of the study sites or Sponsor) with dermatologic or plastic surgery expertise will oversee the safety aspects of this study. Review and MedDRA coding of all AEs and assessment or identification of UADEs will be performed throughout study.

## 6 STATISTICAL METHODS

### 6.1 STATISTICAL AND ANALYTICAL PLANS

#### 6.1.1 Analysis Cohorts

- **Modified Intent-to-Treat (mITT) Cohort:**

The modified intent-to-treat mITT data set will include all enrolled participants that underwent the DH procedure but exclude any roll-in participants. The mITT analysis cohort will be used for all described analyses.

- **Per Protocol (PP) Cohort:**

The PP cohort will be used as a secondary support of the primary effectiveness m-ITT analysis and may be used in exploratory analysis.

The PP analysis set will exclude participants with the following significant protocol deviations:

- 1) Participants with significant violations of the inclusion and exclusion criteria, including:
  - Mild cellulite
  - Impactful co-morbidity outlined in eligibility criteria
  - BMI >30.1
  - Pregnancy or weight gain/loss >10% of baseline weight
- 2) Participants who do not have images for primary effectiveness endpoint (missed, COVID-19, etc.)

Overall, protocol deviations for active participants will be summarized by severity (major/minor), type by visit, and by site. Any deviations or issues reported to IRB/HREC and will be described.

#### **Roll-In and Intent-To-Treat Cohorts:**

All roll-in cohort data will be summarized separately using descriptive statistics. In addition, an intent-to-treat (ITT) data set of all enrolled participants including any roll-in participants that underwent the DH procedure will be analyzed to see whether there is a learning curve that affects the data.

---

 The Investigators without prior Deployable Hook experience will perform up to two (2) roll-in, or “training” procedures.

 The Investigators without prior Deployable Hook experience will perform up to two (2) roll-in, or “training” procedures.

## 6.2 SAFETY ANALYSIS

### 6.2.1 Primary Safety Endpoint

Safety will be demonstrated by the absence of device related Serious Adverse Events (SAEs) directly attributable to the device through 30 days post-procedure. All participants that underwent the index procedure will be included in this analysis.

### 6.2.2 Adverse Events

Procedure-emergent adverse events will be analyzed. All adverse events, new or worsening of pre-existing conditions, starting at the initiation of, or after, the deployable hook procedure, will be summarized. Adverse events will be coded using MedDRA and CTCAE severity grades.

Unless otherwise specified, at each level of participant summarization, a participant is counted once if she reported one or more events. Percentages will be calculated based on the number of participants.

The following specific AE summaries will be generated:

- Overall AEs by study visits, event type, relatedness, ADEs, SAEs, by CTCAE grades
- Grade 3 and higher AEs and related Grade 3 and higher AEs
- SAEs by relatedness (narratives will be provided)
- Unanticipated AEs and UADEs

## 6.3 PRIMARY EFFECTIVENESS ENDPOINT

### 6.3.1 Endpoint Definition

The primary effectiveness endpoint is the change in CSS score at 3 months from baseline. The CSS includes a 6-point (range of 0–5) (Table 8) and will be determined by three (3) independent, blinded physician assessors of participant images obtained before and 3-months after treatment. For clarity, the endpoint will test the mean of the changes for each treated participant, not a 1 point change between mean score of the group at baseline versus 3 months. Success is achieved when the mean change across all treated participants is at least one point.

Long term success: The change in CSS and proportion of responders will be summarized at the 12 month visit. The 95% confidence intervals are intended to support long-term performance claims.

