### 6.3.5 Definition of Success

If the lower bound of the two-sided 95% confidence interval is greater than or equal to 1 then we will reject the null hypothesis and conclude the device performs effectively.

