#### Hypothesis:

- $H_0: D < 1$
- $H_a: D \geq 1,$

where  $D$  = improvement in the CSS score from baseline to 3 months, and 1 is the performance goal.

The endpoint with a sample size of 54 participants will be adequately powered with at least 90% power to test the hypothesis that the mean reduction at 3-months is equal to or greater than 1. This study's sample size will be increased by 25% for a total N of 68 to account for the potential of missed visits amid the pandemic.

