#### 6.5 SECONDARY EFFECTIVENESS ENDPOINTS

Descriptive statistics will be used to summarize the secondary endpoints including mean, standard deviation, median, range for continuous data and frequency and percentage for categories values.

The secondary endpoints will be split into two categories, either Inferential or simply Descriptive. The inferential secondary endpoints will be tested using the hierarchical approach of gatekeeping to ensure the overall alpha for the trial is maintained. Descriptive secondary endpoints will not have any hypothesis testing performed.

In addition to regular annual reports, there are expected to be 3 reports prepared (3-month, 6 month, final – see **Section** Error! Reference source not found.), and the first report will have the 3 month results including the primary endpoint and all inferential secondary endpoints tested. The 6 month and final reports will include 95% confidence intervals for the endpoints that were used in the primary and inferential secondary endpoints for the longer-term visits to provide support for longer-term performance of these same endpoints.

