##### 6.5.1 Hierarchical testing

If the primary endpoint passes, a subset of the secondary endpoints (inferential) will have hypothesis tests performed for potential labeling claims. These endpoints will be tested the specific order presented below. If the first secondary endpoints passes the hypothesis test (rejects the null hypothesis), then the next secondary endpoint will be tested. Testing will continue up to the point that a hypothesis test fails. Endpoints that follow will then simply use descriptive statistics and no p-values will be presented. Since this testing relies first on the primary endpoint

passing, the 6-month data will be used instead should 3-month COVID 19 related missed visits reduce the evaluable data to <54.

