### 6.5.2 Secondary Endpoint 1 (Inferential) – CSS Responders at 3 months

Endpoint Definition: The CSS score at 3 months. A participant is considered a responder if the 3-month CSS score has improved by at least 1 point from the baseline CSS score.

Hypothesis:

Ho:  $p \leq 60\%$

Ha:  $p > 60\%$ ,

where  $p$ =proportion of responders and 60% is the same performance goal that Cellfina used to achieve approval.

Analysis cohort: The mITT cohort.

Statistical Analyses: The count and proportion of responders will be summarized along with an exact binomial 2-sided 95% confidence interval for the proportion of responders along with a p-value.

Definition of Success: If the lower bound of the 2-sided 95% confidence interval is greater than or equal to 0.6 then we will reject the null hypothesis and declare proportion of responders are greater than 60%.

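### Section 6.3.1 words primary success as an observed mean change of at least 1 point, a looser rule than the confidence-bound criterion in 6.3.5

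*Combined protocol and SAP*

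**What the plan says.** Section 6.3.1 (Endpoint Definition) first explains which quantity is tested: "For clarity, the endpoint will test the mean of the changes for each treated participant", as opposed to a difference between the group means at two visits. It then adds "Success is achieved when the mean change across all treated participants is at least one point". No confidence limit is mentioned. The synopsis likewise gives the primary endpoint with a 1-point threshold and no interval.

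Section 6.3.5 (Definition of Success) states: "If the lower bound of the two-sided 95% confidence interval is greater than or equal to 1 then we will reject the null hypothesis". Section 6.3.4 plans that interval together with a Student's t-test, and 6.3.2 sets the hypotheses against a performance goal of 1 (H0: D < 1; Ha: D ≥ 1).

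The gate to the secondary endpoints is in 6.5.1: "If the primary endpoint passes, a subset of the secondary endpoints (inferential) will have hypothesis tests performed for potential labeling claims". For the step from the first secondary endpoint to the next, 6.5.1 says what passing means: "If the first secondary endpoints passes the hypothesis test (rejects the null hypothesis), then the next secondary endpoint will be tested". It gives no such explanation for the primary endpoint. Section 6.5 states the purpose of the scheme: the inferential secondary endpoints "will be tested using the hierarchical approach of gatekeeping to ensure the overall alpha for the trial is maintained". Each of the three has its own success definition based on an interval limit, for example in 6.5.2: "If the lower bound of the 2-sided 95% confidence interval is greater than or equal to 0.6 then we will reject the null hypothesis".

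**The concern.** The plan contains two statements of primary success with different thresholds. One compares the sample mean with 1. The other compares the lower 95% limit with 1. In a single-arm study against a fixed performance goal, this rule carries the whole confirmatory claim, so it should be stated once and in one form.

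The consequence runs through the gate. If the 6.3.1 sentence were applied as written, an observed mean just above 1 would count as a pass and open the labeling-claim tests although the primary null had not been rejected. A gate that opens on a point estimate cannot give the alpha protection that 6.5 claims for it. Leaving both sentences in place also lets someone argue, once the data are known, that a mean slightly above 1 was prespecified success.

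**Working it through.** **Inputs from the plan.** Performance goal 1 (6.3.2); two-sided 95% interval and t-test (6.3.4), hence one-sided 0.025; 54 evaluable participants and at least 90% power (6.3.7); total N 68 (6.3.7).

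**Assumption.** The plan gives neither an SD for the change in CSS nor the mean assumed for the sample size. I use SD 0.8 to 1.0, with 0.5 to 1.5 as a wider range.

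**The plan's own figures.** The inflation reproduces: 54 × 1.25 = 67.5, rounded up to 68. The 90% power at N = 54 can be neither reproduced nor refuted without a mean and SD. It can be solved for the effect it implies. For a one-sample t-test at one-sided 0.025, (D − 1)/SD = 0.449, so D = 1 + 0.449 × 0.8 = 1.36 or 1 + 0.449 × 1.0 = 1.45. Section 6.3.7 used a Wilcoxon test; scaling n by 3/π for normal data gives 0.460, so D = 1.37 or 1.46. A design mean this far above 1 fits the interval rule.

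**Step 1: observed means on which the two rules disagree.** The 6.3.5 rule needs an observed mean of at least 1 + t(0.975, n−1) × SD/√n. The 6.3.1 sentence needs only 1.

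| n | t | SD 0.5 | SD 0.8 | SD 1.0 | SD 1.5 |
|---|---|---|---|---|---|
| 54 | 2.0057 | 1.14 | 1.22 | 1.27 | 1.41 |
| 68 | 1.9960 | 1.12 | 1.19 | 1.24 | 1.36 |

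For example, at n = 54 and SD 0.8: 2.0057 × 0.8/√54 = 0.218. Observed means from 1.00 up to the tabled value succeed under 6.3.1 and fail under 6.3.5.

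**Step 2: false success at the edge of the null.** P(mean ≥ 1) comes from the normal distribution and P(lower limit ≥ 1) from the noncentral t.

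- True mean 1.00: 0.500 against 0.025, for every SD and both sample sizes.
- True mean 0.999, n = 54, SD 0.8 / 1.0: 0.496 / 0.497 against 0.0245 / 0.0246. This case lies inside the stated null.
- True mean 0.90, n = 54, SD 0.8 / 1.0: 0.179 / 0.231 against 0.002 / 0.004.

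The CSS is discrete, so I also looked at simulated integer changes with a true mean of 1 (n = 54, 200,000 trials). The point rule passed in 51% to 53% and the interval rule in 2.5%.

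**Step 3: disagreement at the design effect.** At n = 54, 0.449 × √54 = 3.30, so P(mean ≥ 1) = 0.9995. The interval rule passes in 0.900, so the verdicts differ in 0.0995 of trials. That is essentially the type II error of the planned test. With all 68 evaluable at the same effect, the interval rule passes in 0.955 and the verdicts differ in 0.045.

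**Step 4: which rule the text supports.** Section 6.3.5 is the only place that says when the primary null is rejected. Section 6.3.4 produces the interval it needs, 6.3.7 powers a superiority test against the margin, and all three inferential secondary endpoints use a lower limit under the same kind of label. The synopsis wording reads as an endpoint label, not a decision rule. On the other side stands the 6.3.1 sentence, which is phrased as a condition for success and describes the mean over the treated sample.

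**The case against.** The strongest reply is that the plan resolves this itself. Section 6.3.5 carries the title for success definitions and gives an explicit rejection rule, while 6.3.1 defines the endpoint. A specific rule under its own title normally governs a descriptive sentence elsewhere. The 6.3.1 sentence follows a clarification about which mean is tested, and may only restate Ha: D ≥ 1. Section 6.3.7 uses similar words for the hypothesis, describing the study as "adequately powered with at least 90% power to test the hypothesis that the mean reduction at 3-months is equal to or greater than 1". On the gate, 6.5 treats the primary as a tested endpoint and 6.5.1 speaks of hypothesis tests throughout, so opening it on a bare mean would mean disregarding several sections together. The synopsis also leaves out the decision rules for the secondary endpoints, so its silence on the interval is a matter of style. Finally, the contrast of 50% with 2.5% holds for any point-estimate rule against any 95% interval rule and is not specific to this trial.

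Most of this stands. It makes 6.3.5 very likely the intended rule, and it means the figures above bite only if the 6.3.1 sentence is applied as written. It does not remove the sentence. The clarification before it already names the quantity, and the sentence then goes further and says when success is achieved. Nothing ranks it below 6.3.5, and nothing expressly ties the primary gate in 6.5.1 to 6.3.5.

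**Conclusion.** The point holds and is minor. Section 6.3.1 states a success threshold for the primary endpoint that is looser than the criterion in 6.3.5 and wrong as a success rule. The planned analysis itself is not at fault, and under 6.3.5 alpha is controlled as intended.

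Applied literally at 54 evaluable participants, the 6.3.1 wording would reverse the verdict for observed means from 1.00 to about 1.22 to 1.27 (1.14 to 1.41 over the wider SD range). It would raise the false-success rate at the null boundary from 2.5% to about 50%. The ranges of observed means rest on assumed SDs. The 50% and 2.5% do not depend on the SD, but the 50% assumes roughly symmetric changes.

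**What to change.** Replace the success sentence in 6.3.1 with one to this effect: *success is achieved when the lower bound of the two-sided 95% CI for the mean change is at least 1 (see 6.3.5)*. If the sponsor prefers to keep the rule in one place only, deleting the sentence and cross-referring to 6.3.5 serves equally well. Have the synopsis refer to the same criterion. In 6.5.1, state that the primary endpoint passes when the 6.3.5 criterion is met.

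The cost is wording only. The sample size, power and planned analysis stay as they are, and 6.3.1 becomes exactly as strict as 6.3.5 already is.

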**Table 8 Cellulite Severity Score**

Severity scoring by the independent, blinded assessors	
PART A- Number of evident depressions	
0	None
1	Mild ( $\leq 4$ depressions)
2	Moderate (5 to 9 depressions)
3	Severe ( $\geq 10$ depressions)
PART B – Average depth of depressions	
0	None
1	Mild (1-2 mm)
2	Moderate (3-4 mm)
3	Severe ( $\geq 5$ mm)
TOTAL CSS SCORE	$=(\text{PART A} + \text{PART B}) - 1$
One CSS is rendered per participant. Part A is the number of depressions across all treated regions, and Part B the average across all treated regions. This study does not prescribe if participant treated unilaterally or bilaterally.	

**6.3.2 Hypothesis**

Ho:  $D < 1$

Ha:  $D \geq 1$ ,

where  $D$  = reduction in the CSS score from baseline to 3 months, and 1 is the performance goal.

**6.3.3 Analysis cohort**

The mITT cohort will be the primary analysis, but supplemental analysis will also be performed using the PP cohort.

**6.3.4 Statistical Analyses**

The reduction in CSS will be calculated and descriptive statistics including mean, standard deviation, median and range will be summarized. The 2-sided 95% confidence interval for the mean reduction in CSS will be calculated along with the corresponding p-value (Student's t-test).

 CSS = CSS-A (Number of Evident Depressions) + CSS-B (Average Depth of Depressions) – 1

### 6.3.5 Definition of Success

If the lower bound of the two-sided 95% confidence interval is greater than or equal to 1 then we will reject the null hypothesis and conclude the device performs effectively.

### 6.3.6 COVID-19 Contingency

As outlined in section Error! Reference source not found., before blinded photometric evaluation of CSS, the number of participants with images available for the 3-month endpoint will be confirmed. If the number of participants with images cannot adequately power the endpoint (N=54) due to excessive 3-month COVID 19 related missed visits, the primary endpoint time point will be changed to 6-month. Of note, the inferential secondary endpoints will similarly change to 6-month (section 6.5).

### 6.3.7 Determination of Sample Size

Sample size calculations were estimated using PASS 14 (Kaysville, Utah, USA), using Wilcoxon Signed Rank test for superiority by a margin (the more conservative approach compared to t-test)

#### Hypothesis:

- $H_0: D < 1$
- $H_a: D \geq 1,$

where  $D$  = improvement in the CSS score from baseline to 3 months, and 1 is the performance goal.

The endpoint with a sample size of 54 participants will be adequately powered with at least 90% power to test the hypothesis that the mean reduction at 3-months is equal to or greater than 1. This study's sample size will be increased by 25% for a total N of 68 to account for the potential of missed visits amid the pandemic.

### 6.3.8 Poolability Analysis

Analyses of the primary effectiveness endpoint will be performed to assess the comparability of study sites. Sites with fewer than 5 participants each will be pooled into a composite site.

Change in CSS will be analyzed by ANOVA to assess if the improvement in CSS differs among study sites. If the study sites have a difference ( $p < 0.15$ ), then additional analyses will be performed to explore the cause of the difference, in particular, if the differences are caused by differences in some baseline factor.

### 6.3.9 Covariate Adjustment and Exploration

An ANCOVA model, which allows adjusting for covariates, will be used on the 3-month endpoint to uncover important prognostic factors. If any of the following factors: age, race, baseline BMI, indicator variable of change in body weight of  $\pm 10\%$  (compared to baseline), or, number of regions treated are not significant ( $p\text{-value} \geq 0.10$ ), they will be dropped from the

model. This is not intended to be the primary analysis of the 3-month endpoint, it is only an exploratory analysis that will be used to look for possible important prognostic factors. This analysis may be repeated on the change in CSS data at 6 and 12-month visits once data are complete.

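### The exploratory ANCOVA for prognostic factors leaves out baseline CSS, so it cannot test baseline severity or tell it apart from number of regions treated; one listed factor is also measured after treatment

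*Combined protocol and SAP*

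**What the plan says.** Section 6.3.9 (Covariate Adjustment and Exploration) describes an ANCOVA on the 3-month endpoint whose purpose is "to uncover important prognostic factors". The endpoint, defined in 6.3.1, is change in CSS from baseline.

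The candidates are "age, race, baseline BMI, indicator variable of change in body weight" of ±10%, the change being "compared to baseline", and number of regions treated. If any of the factors up to and including "number of regions treated are not significant", meaning p ≥ 0.10, "they will be dropped from the" model. The section says of the analysis that "it is only an exploratory analysis that will be used to look for possible important prognostic factors". It may be repeated at 6 and 12 months.

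Table 8 defines the score: "Part A is the number of depressions across all treated regions", and Part B is the average depth over those regions.

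Section 6.3.8 (Poolability Analysis) says: "Change in CSS will be analyzed by ANOVA to assess if the improvement in CSS differs among study sites". If site differences reach p < 0.15, further analyses look for the cause, including differences in an unspecified baseline factor.

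Mean baseline CSS is tabulated in the learning-curve summaries (6.6.1). It is not placed in any model.

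**The concern.** In a search for predictors of change in a bounded severity score, the starting score is the obvious first candidate, and it is missing here. Two features of the plan make the gap matter.

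- **Ceiling on improvement.** CSS runs from 0 to 5, so a participant who starts at 3 can improve by at most 3 points and one who starts at 5 by at most 5.
- **Overlap with a listed factor.** Treating more regions gives more area in which depressions are counted, so number of regions tends to move with baseline Part A.

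If the regions term is kept, the reader cannot say whether extent of treatment or baseline severity is responsible. If it is dropped, baseline severity has still not been examined.

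The weight-change indicator is a different problem. It is known only after treatment, so it cannot describe a patient's prognosis at baseline, and conditioning on it can distort the other coefficients. What is at stake is how the exploratory findings are interpreted.

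**Working it through.** **The plan's own figures.** The documents give no number for this model. The sample sizes used below are the evaluable 54 and the total 68 from 6.3.7; 54 × 1.25 = 67.5, rounded up to 68, reproduces the plan's total.

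**Inputs not in the documents (assumed).** Let a be the correlation of a factor with baseline CSS and b the correlation of baseline CSS with change. Each is taken from 0.2 to 0.5. The factor has no effect on change once baseline CSS is known.

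**Retention without baseline CSS.** The factor's correlation with change is r = a × b. The test statistic is shifted by δ = r√n / √(1 − r²), and the chance of p < 0.10 is about Φ(δ − 1.645) + Φ(−δ − 1.645).

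Example for a = b = 0.4, n = 54: r = 0.16; δ = 0.16 × 7.348 / 0.987 = 1.19; chance = Φ(−0.45) + Φ(−2.84) = 0.325 + 0.002 = 33%.

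The simulated columns come from normal-data regressions of change on the factor, 10,000 trials per setting (Monte Carlo standard error at most 0.5 percentage points).

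| a, b | r | δ (n = 54) | formula, n = 54 | simulated, n = 54 | formula, n = 68 | simulated with baseline added, n = 54 |
|---|---|---|---|---|---|---|
| 0.2, 0.2 | 0.04 | 0.29 | 12% | 12% | 12% | 10% |
| 0.2, 0.3 | 0.06 | 0.44 | 13% | 14% | 14% | 10% |
| 0.3, 0.3 | 0.09 | 0.66 | 17% | 17% | 19% | 10% |
| 0.4, 0.4 | 0.16 | 1.19 | 33% | 31% | 38% | 11% |
| 0.5, 0.4 | 0.20 | 1.50 | 44% | 43% | 52% | 10% |
| 0.5, 0.5 | 0.25 | 1.90 | 60% | 58% | 69% | 10% |

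With a = 0 or b = 0 the simulated rate stays at about 10%.

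**Check on a more literal model.** Baseline CSS was limited to 3, 4 or 5, regions to 1 to 6, with age, race and BMI also in the model and an assumed residual SD of 0.8. At n = 54 and a slope of 0.5 per baseline point, the regions term was wrongly kept 20%, 37% and 58% of the time when its realised correlation with baseline CSS was about 0.26, 0.44 and 0.62. At a slope of 0.75 the figures were 26%, 55% and 84%. If the slope or the correlation was zero, the rate was about 10%.

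**What rating error does to the adjusted model.** The last column of the table assumes baseline CSS is measured without error. Now let true change D be independent of true baseline T, with independent rating error at each visit. Observed baseline is T + e and observed improvement is D + e − e′. With assumed reliability 0.6 to 0.8, factor-to-T correlation 0.4 or 0.5, and SD of D from 0 to 1 in units of the SD of T, n = 54:

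- without baseline CSS, the null factor is kept 9% to 11% of the time;
- with baseline CSS, it is kept 14% to 44% of the time. Other runs at assumed reliability 0.6 to 0.8 gave about 13% to 59%.

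The reason is that, at a given observed baseline, a higher factor value implies a higher T and so a smaller e, which lowers the observed improvement. Neither model is safe on its own.

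**Weight-change indicator.** If 1% to 5% of participants changed weight by 10% or more (assumed), that is 54 × 0.01 = 0.5 to 54 × 0.05 = 2.7 participants, so the term would also be barely estimable.

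**The case against.** The strongest reply is that nothing confirmatory rests on this model. Section 6.3.9 says so itself, and the primary t-test, success rule, sample size and hierarchical tests do not use it. That stands, and it sets the severity. The screen is also loose by design: five independent null factors tested at 0.10 give 1 − 0.9⁵ = 41% for at least one false flag.

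Other points on that side:

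- **The regions link may be weak.** Part A stops at 10 or more depressions, Part B is an average, and entry needs at least 5 depressions and CSS ≥ 3, which narrows the baseline range. This stands and is why the range starts at 0.2; the link could be weaker still.
- **A factor that acts through severity is still prognostic.** This is fair. A reader might infer that a retained regions term would be a false finding. The documents do not support that, since 6.3.9 claims no independent or causal effects. What they do show is that the term could not be interpreted separately from baseline severity.
- **Adjustment is not a cure.** A reader might infer that adding baseline CSS restores a 10% error rate. That holds only if the score is free of rating error, which cannot be assumed for a photograph-rated ordinal scale.
- **Site comparison.** A reader might infer that 6.3.8 has the same defect. It does not in full, because a site difference at p < 0.15 already triggers a search for a baseline cause. What remains is that the baseline factor is not named.
- **Weight change.** A reader might infer that this indicator contributes to the confusion with baseline severity. It does not; that comes from the omitted score. The per-protocol cohort already excludes weight change above 10%, so a related sensitivity analysis exists.
- **The factor list may not be exhaustive.** An ANCOVA could be meant to carry the baseline score, and this is an abbreviated protocol. The text does not say so, and one added clause would settle it.

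**Conclusion.** The point holds as a minor gap in specification. Two facts rest on the text alone: baseline CSS is not among the named factors of a model built to find prognostic factors for change in CSS, and the weight-change indicator is measured after treatment. It follows that the model as written cannot test baseline severity and cannot separate it from number of regions treated.

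The size is conditional. For assumed correlations of 0.2 to 0.5 on both links, a factor with no effect of its own is kept about 12% to 58% of the time at n = 54, against a nominal 10%. Stronger assumed links give more, and a zero link gives no inflation. The documents supply none of these inputs, so the percentages are illustrations, not predictions. Adjusted and unadjusted results may differ in either direction, so neither should be presented alone.

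The documents do not support any inference that the trial's effectiveness conclusion is at risk.

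**What to change.** 1. In 6.3.9, add evaluator-scored baseline CSS to the ANCOVA and exempt it from the p ≥ 0.10 drop rule. Because Table 3 has baseline images in every evaluation session, state which session's baseline score is used.
2. Report the factor results with and without baseline CSS, and note that rating error can make them differ.
3. Take the ±10% weight-change indicator out of the prognostic model and show it as a separate sensitivity analysis.
4. In 6.3.8, name baseline CSS as a baseline factor to examine in the existing follow-up step. The site ANOVA itself can stay as it is.

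The cost is one more model term, one more table and a few lines of text. No new data are needed, since change in CSS cannot be computed without the baseline score.
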